During the study appointment, a bilingual RA will 1) obtain HIPAA authorization to review the adolescent patient's EMR, and 2) instruct the participant on how to use either the English or Spanish version of the tablet application. For Aims 1a and 2, the study appointment will last about 60 minutes and will be audio-recorded. For Aims 1b and 3, pre-clinic visit study activities will take 10-20 minutes; post-visit activities will take another 20-25 minutes. All study staff will be trained by Drs. [name] and [name]. Parent participants will receive a \$50 honorarium in the form of a gift card.

We will conduct study visits with a total of 369 parent participants. We expect very few parents will be fathers (<5%; n = 19) and have powered our analysis to only analyze data from mothers of adolescent patients (n = 350). For Aim 1, we will enroll 106 parents: 53 for formative research on self-generated arguments (Aim 1a), and 53 to characterize parent-provider discussions about the HPV vaccine (Aim 1b). For Aim 2, 168 parents will be enrolled for self-persuasion intervention conditions comparing levels of choice and cognitive processing. We will enroll 95 parents for Aim 3, recording provider/patient interaction and testing of tablet-based application. We expect to enroll 18 providers in order to audiorecord the parent-provider discussions for Aims 1b and 3.

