### **Additional Procedures for Each Stage**

**Stage 1:** To accomplish Aim 1a, we will recruit 42 parents of unvaccinated adolescents and 11 parents of adolescents who *have* started the series to gather the full range of arguments for HPV vaccination (n=53, stratified by sex). During a 1-hour study session, a bilingual RA will obtain informed consent and show the parent how to use a tablet-based application. A short video will provide HPV vaccine information suited for parents of adolescent females and males. Then the RA will use a series of questions to prompt parents to verbalize as many pro-vaccine arguments as they can. Afterward, the RA will use a cognitive interviewing-based guide to probe about the self-generated arguments. Parents will then be asked to listen to, rate, and choose among *peer-generated* arguments. The RA will ask questions to clarify whether peer-generated arguments are clear and understood. Finally, participants will be given the entire set of arguments. We will use probes to determine whether they can distinguish among and select their preferred arguments.

To accomplish Aim 1b, we will identify parents of unvaccinated adolescents with upcoming appointments at the 3 neighborhood and 3 school clinics that see the most adolescents. At least 5 parent-child dyads per provider will be recruited (n=53). We will only record discussions between parents and providers who are language concordant. Audiorecording equipment will be set up in the clinic room; research staff will not be present during discussions. After the participant meets with the provider and is discharged, the RA will conduct a 10-minute interview. Parents will be asked open-ended questions about their prior experience with this provider and whether the HPV vaccine was discussed during the visit. Then, we will administer a survey about provider recommendation, HPV vaccine benefits and barriers, and perceived involvement in medical care.

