**Stage 2:** To accomplish Aim 2, we will randomly assign 168 undecided parents (of 84 girls & 84 boys) to 1 of 4 intervention conditions that differ by levels of cognitive processing and choice. In a 1-hour study session, parents will use a tablet-based application that directs them to either: verbalize their own arguments based on topics they choose (deep processing, high choice), verbalize arguments based on topics assigned to them (deep processing, low choice), listen to arguments based on topics they choose (shallow processing, high choice), or listen to arguments based on topics assigned to them (shallow processing, low choice). We will conduct exit interviews to assess parents' perspective on the tablet application, self-persuasion condition, and how their beliefs and experiences shape feelings about the HPV vaccine. Adolescents who accompany their parent to the study appointment at their Parkland clinic will have the opportunity to receive the 1st HPV vaccine dose from a Parkland nurse immediately after the exit interview. We will synthesize quantitative and qualitative data to select the optimal intervention condition for that will be used in Stage 3.

**Stage 3:** To accomplish Aim 3, we will recruit from pediatric neighborhood and school-based clinics, with a target of 15 parents per site (n=95). Parents will be randomly assigned to either: 1) self-persuasion plus information (optimal intervention condition from Aim 2; n=48), or 2) HPV information only (n=47). For the self-persuasion group, we will follow procedures in Stage 1. Parents in the information only group will be given a tablet and instructed to listen to information about HPV infections and the benefits and risks of the HPV vaccine. We will audiorecord the parent-provider discussion. Immediately after the visit, an RA will conduct an exit interview in which participants will be asked questions about their experiences using the tablet and their communication with the provider.

We expect to review the medical records of 369 adolescents whose parents were enrolled in our study. Medical records will be reviewed after 12 months for HPV vaccine dates. We will also abstract info for 3 other vaccines (TDAP, MCV4, & influenza) that are correlated with HPV vaccination.

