### Analysis Plan for Aim 1b:

**Coding and Analyses of Audiorecordings.** We will modify [name]'s Active Patient Participation Coding scheme, a well-validated observational tool for behavior coding, to code audiorecordings of parent and provider participation in HPV vaccine discussions. [name], a recognized health communication expert will consult with the team on categories relevant to parents' participation about immunizations. We will measure both parent and provider communication outcomes.

For parents, three types of *active* communication will be captured—1) asking questions, 2) assertive expressions (offering preferences, making a request), and 3) expressing concerns (worries, seeking reassurance). Active

“verbalizations” are those that influence discussion content and provider’s beliefs and behaviors. Drs. [name], [name], and [name] will train RAs how to assign verbal utterances according to the categories above. Summary scores of the total number in each category per patient per interaction will be generated. Statements to both nurses and physicians will be counted, as nurses are often involved in vaccine discussions. We will use the phrasing used by parents to inform the content of arguments in Stage 2. For example, parents may express important values (e.g., best interest of my child), concerns, or hesitations that can help us craft relevant, easy to understand arguments.

For providers, we will assess: 1) vaccine recommendations; 2) provision of information about immunizations and HPV vaccine (three types of utterances: description, benefits, and risks); 3) partnership building (open-ended questions encouraging patients to share opinions, feelings, ask questions, and participate in decision-making); and 4) supportive talk (verbal statements of reassurance, empathy, or sensitivity).

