Coders will co-code 5 recordings to establish rating agreement, and will code 3 more recordings semi-independently engaging in discussion to resolve differences. To evaluate inter-coder reliability, we will use Krippendorf’s alpha, a measure of agreement that allows for the analysis of categorical and continuous variables in the presence of missing data. To describe the communicative environment, we will compute means, standard deviations, and ranges of parent and provider communications. To explore the effect of provider discussions, we will compare parents’ responses to baseline and exit survey items regarding vaccine benefits and barriers (decisional balance), and post-visit perceived involvement in care.

**Qualitative Data Analysis.** Interviews will be audiotaped and transcribed. Drs. [name], [name], and [name] will perform in-depth analysis of all transcripts using NVivo 9.0 (QSR International). Data will be analyzed within and across transcripts. Through iterative coding and interpretation, the team will code actual utterances, expressions and concepts against participant characteristics to identify themes and relationships. We will organize these codes into a codebook that relates data to behavioral theory. Regular meetings will enable the team to test emergent themes and interpretation against the knowledge base of experts in pediatrics (e.g. [name], [name]), self-persuasion ([name]), vaccination ([name]), and intervention development ([name]).

**At the end of Stage 1, we will know:** (1) the range of pro-vaccine arguments underserved parents generate, (2) which arguments are easiest to generate, most prevalent, and persuasive, and (3) range and degree to which parents participated in HPV vaccine discussions. We will also know which peer-generated arguments are rated as clear, comprehensible, and distinct from other arguments. With these data, we will select the most prevalent argument topics with easy-to-generate arguments for the self-persuasion intervention conditions in Aim 2. Baseline descriptive information about the communicative environment will be compared with parent-provider discussions after exposure to the optimal self-persuasion intervention in Aim 3.

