### **Aim 3. Examine feasibility of the optimal intervention (identified in Aim 2) with a pilot study (n = 90) in the safety-net clinics.**

**Analysis Plan for Aim 3:** We will obtain information on the following outcomes that will be important for developing a subsequent efficacy randomized controlled trial (RCT).

**Enrollment rates.** We will assess whether enrollment rates are similar across the clinic sites.

**Sufficient time for intervention procedures.** Because clinic sites may differ in their patient flow and visit wait times, we will track the number of participants who complete the tablet-based procedure within the time constraints allowed by the clinic and determine whether time allotted for completing the intervention is similar and sufficient across all sites. We expect an 85-90% completion rate to determine feasibility.

**Potential for contamination.** We will determine the appropriate level of randomization (patient, provider, or clinic) and the degree to which contamination occurs at each level. We will use visit history data in the EMR to examine the percentage of patients who visit more than one clinic and see more than one provider. For example, if there is significant crossover of patients to different providers at the same clinic, then we will randomize at the clinic-level in the subsequent efficacy trial.

**Intermediate outcome – active parent participation.** We hypothesize that exposure to the self-persuasion intervention will positively influence active parent participation in discussions with providers. We will apply [name]'s scheme to code the 3 types of active communication (Aim 1b). To estimate effect sizes for the subsequent efficacy RCT, we will compute means, standard deviations, and ranges of parent and provider communications and compare them to data collected in Aim 1b. We will use multivariable mixed linear regression modeling to explore factors associated with parent degree of participation (e.g., English vs. Spanish language). This method models the provider as a random effect to adjust for potential clustering of patients by provider; parent/patient characteristics of interest will be modeled as fixed effects.

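### Stage 3 parent participation is coded by research assistants with no masking to arm, and no independently coded set covering Stage 3 is specified for Krippendorff's alpha

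*Combined protocol and SAP*

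**What the plan says.** All references are to the combined protocol and SAP.

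- **Who codes.** Under Analysis Plan for Aim 1b, the investigators "will train RAs how to assign verbal utterances according to the categories above". The parent categories are asking questions, assertive expressions and expressing concerns, summed per interaction.
- **Who meets the parent.** Under Study Procedures, a bilingual RA at the study appointment will "instruct the participant on how to use either the English or Spanish version of the tablet application". For Stage 3, Additional Procedures for Each Stage adds that after the visit "an RA will conduct an exit interview in which participants will be asked questions about their experiences using the tablet".
- **Multi-coder work.** Under Analysis Plan for Aim 1b, "Coders will co-code 5 recordings to establish rating agreement", and they then "will code 3 more recordings semi-independently engaging in discussion to resolve differences". The next sentence names Krippendorff's alpha for inter-coder reliability, described as "a measure of agreement that allows for the analysis of categorical and continuous variables in the presence of missing data". It does not say which recordings alpha uses, whether codes are taken before or after discussion, or what value is acceptable.
- **Use in Stage 3.** Under Analysis Plan for Aim 3, Intermediate outcome: "We hypothesize that exposure to the self-persuasion intervention will positively influence active parent participation". The Aim 1b scheme is applied again. Means, standard deviations and ranges are computed to give effect sizes for the efficacy trial and are compared with Aim 1b. No double-coding is described there.

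**The concern.** There are two separate issues.

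**Masking.** Deciding whether a remark is an assertive expression or a concern takes judgement. A coder who knows the arm and expects self-persuasion to raise participation can lean that way without intending to. Any such lean adds directly to the estimated effect, and that estimate is meant to help design the next trial.

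**Reliability.** The text leaves open what alpha will be computed on. If it uses codes already reconciled by discussion, it measures agreement after correction, not the agreement to be expected when coders work alone. If it uses Aim 1b recordings only, it says nothing about coding in Stage 3, where the hypothesis is examined.

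**Working it through.** The plan gives no power, reliability target or sample size for the coding, so there is no figure of its own to reproduce. The steps below are counts from the documents, then illustrations under stated assumptions.

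**1. Counts.** Recordings with more than one coder: 5 + 3 = 8. Aim 1b has 53 recordings. Stage 3 has 48 + 47 = 95. Together that is 53 + 95 = 148.
- 8/53 = 15.1% of Aim 1b, the section in which the 8 are described.
- 8/148 = 5.4% of both stages.
- Stage 3 recordings described as double-coded: 0 of 95.

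**2. Safeguards set beside what would be needed.**

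| Provision | Section | Hides arm from coder? |
|---|---|---|
| Staff not in the room during the discussion | Additional Procedures (Stage 1) | No; an RA sees the parent before and after |
| Data carry a study ID | Procedures to Maintain Confidentiality | Not stated |
| Identifiers removed from transcripts | Recruitment Methods, Providers | No; this concerns identity |
| Training on collecting data free from bias | Special Precautions | No |

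No section separates coding RAs from those who meet parents.

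**3. Effect of a coding shift.** Assume no true effect, a two-sided 5% test, and coding that favours self-persuasion by b SD. The standard error is √(1/48 + 1/47) = 0.205 SD. The rejection rate is 1 − Φ(1.96 − b/0.205) + Φ(−1.96 − b/0.205).

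| b (SD) | Rejection rate |
|---|---|
| 0 | 5.0% |
| 0.1 | 7.8% |
| 0.2 | 16.4% |
| 0.3 | 31.0% |

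The plan names no such test for this outcome, so the more direct consequence is the estimate itself, which moves by b. For example, suppose the true effect is 0.40 and b = 0.2, so that 0.60 is reported (0.60 is the size the Background cites for exercise intentions). Required sample size goes as 1/d², so the next trial would be sized at (0.40/0.60)² = 44% of what it needs.

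**4. Effect of post-discussion codes on alpha.** Assume two coders, normal scores with total variance 1 and true reliability ρ, and discussion that moves each coder halfway to the pair mean. For interval data, alpha = 1 − Do/De, where Do is the mean squared difference between coders and De is twice the total variance. At ρ = 0.6:
- Independent: Do = 2 × 0.4 = 0.8 and De = 2, so alpha = 0.60.
- After half-resolution: Do = 0.8/4 = 0.2 and De = 2 × (0.6 + 0.2 + 0.05) = 1.7, so alpha = 1 − 0.2/1.7 = 0.88.

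Simulation with 8 recordings (8,000 runs) agrees:

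| ρ | Median alpha, independent | Median alpha, half-resolved | P(alpha ≥ 0.8), independent | P(alpha ≥ 0.8), half-resolved |
|---|---|---|---|---|
| 0.5 | 0.48 | 0.84 | 6% | 61% |
| 0.6 | 0.57 | 0.87 | 12% | 74% |
| 0.7 | 0.68 | 0.91 | 23% | 86% |

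**5. Precision of an independent sample.** Of 148 recordings, 15% is 22 and 20% is 30. For an assumed intraclass agreement of 0.80 with two coders, F = (1 + 0.80)/(1 − 0.80) = 9. The 95% limits are (F' − 1)/(F' + 1), where F' is 9 divided by F(0.975; n−1, n) for the lower limit and 9 multiplied by F(0.975; n, n−1) for the upper.
- n = 8: 0.33 to 0.96
- n = 22: 0.58 to 0.91
- n = 30: 0.62 to 0.90

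**The case against.** **The 8 recordings look like calibration.** This stands. The first 5 are coded to establish agreement, the next 3 are discussed, and alpha comes in a separate sentence. A reader might infer that alpha can only come from those 8, but the plan does not say so. Semi-independent coding also leaves room for scores recorded before discussion. What remains is that no independently coded set is named.

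**The fraction is not the problem.** A reader might take 5.4% as the shortfall. The 8 belong to the Aim 1b plan, where they are 15.1%. The valid complaint is that no reliability check is described for Stage 3.

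**The intervals in step 5 do not show overstatement.** They show imprecision, under an assumed 0.80 and with the recording as the unit. If alpha is computed on single utterances, they do not apply. They serve here only to judge the proposed sample.

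**Few double-coded recordings do not inflate an arm contrast.** This also stands. Random coder error shrinks a standardised difference: 0.60 × √0.6 = 0.46 at reliability 0.6. Only coding that differs by arm can inflate it.

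**Knowledge of arm is not shown.** In part. The documents show a shared role, not shared individuals, and do not say that files carry an arm label. Training differs by job description (Data Management). But none of the safeguards listed excludes knowledge of arm, and the plan does not otherwise provide for masking.

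**This is an intermediate outcome in a feasibility pilot, coded with an adaptation of a validated scheme.** True, and it limits the weight of the point.

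**Conclusion.** The point holds as two gaps in the specification: coders are not masked to arm for an outcome that needs judgement and has a directional hypothesis, and no independently coded set that includes Stage 3 is specified for alpha. The first could bias the participation effect size towards self-persuasion. The second means that alpha would overstate agreement if it were computed on post-discussion codes, and would not cover Stage 3 unless recordings from that stage were added.

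The sizes in the working rest on assumed coding shifts, reliability levels and half-resolution of differences. They show what could happen, not what will.

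A reader might go further and conclude that the trial's main result is at risk. The documents do not support that, because HPV vaccine uptake is taken from the EMR and does not depend on the coding. This is a cheap improvement, worth making because the participation estimate is carried into the efficacy trial.

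**What to change.** 1. Give each Stage 3 recording a file ID that does not show arm, and assign it to an RA who did not run that session. State this in Analysis Plan for Aim 3.
2. Treat the 8 jointly coded or discussed recordings as training and leave them out of the reliability estimate.
3. Draw a random 15-20% of Aim 1b and Stage 3 recordings, have RAs code them independently, and compute alpha on scores recorded before any discussion. Sampled in proportion, this is about 8-11 of the 53 Aim 1b recordings and 14-19 of the 95 from Stage 3, or 22-30 in all. State whether the unit is the utterance or the recording's summary score.

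**Cost.** A second coding of roughly 22-30 recordings by existing RAs; an ID without arm costs next to nothing. The plan does not give the number of RAs. Double-coding a Stage 3 recording needs two who did not run that session, so the rota should be checked.

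**Limits.** Talk in a recording may still reveal the arm. Masking arm does not by itself protect the comparison of Stage 3 with Aim 1b, which stays open to coder drift and to knowledge of the stage.

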### **Analysis Plan for Aim 2:**

**Quantitative Analysis.** Data will initially be examined using univariate statistics and graphical techniques. Continuous measures will be described using medians, means, and standard deviations; dichotomous variables will be summarized as proportions. Across self-persuasion conditions, demographic characteristics will be compared at baseline via two-way ANOVA or chi-square tests, as appropriate. If groups differ on any of these variables, further analyses will be conducted both with and without these variables as covariates to determine whether these demographic variables are of relevance to group differences.

We will compare the effects of choice and cognitive processing on vaccination intentions (primary outcome) using linear regression. Independent variables will be dummy-coded variables based on two main effects (choice: high = 0, low = 1; processing: deep = 0; shallow = 1), plus their interaction. If equivalence assumptions of initial scores and parallel regression slopes for the groups are met, baseline intentions will be included as a covariate to properly model change. If not, repeated measures ANOVA will be used. We anticipate changes in intentions will be

highest in the deep processing, high choice condition, indicating an additive effect. We will also explore the interaction of the two effects. We will use a similar analytic strategy to examine the effects of choice and processing on decisional balance (secondary outcome).

**Vaccination rates.** Using eligibility data, we will assess whether vaccination rates are similar across all clinic sites.

**Qualitative Data Analysis.** We will use the same analytic process described in Aim 1b.

**Synthesis of Quantitative and Qualitative Analyses.** To determine which self-persuasion condition (1, 2, or 3) is optimal for our safety-net population and will be tested in Stage 3, we will triangulate quantitative and qualitative findings by creating a summary profile for each condition. The optimal condition will be one that has a positive effect on intentions, but also minimizes participants' negative reactions to using the tablet application. A condition that does not affect intentions will not be considered optimal, regardless of its effect on other quantitative and qualitative outcomes. Likewise, a condition that affects intentions but for many participants raises new concerns, is rated as difficult to complete, or takes significant time to complete will not be considered optimal. Drs. [name] and [name] will jointly make this decision in consultation with the team.

**At the end of Stage 2, we will have quantitative and qualitative data that clarify whether it is best to ask parents to verbalize their own arguments, to choose argument topics they prefer, or both, and which self-persuasion condition is optimal in our underserved, safety-net population.** Evidence clarifying which of the two specific mechanisms (deep processing, choice) has an effect, or whether they have an additive effect, will be critical to how we select the optimal self-persuasion condition to implement in Stage 3. For example, if there is an effect of processing but not choice, we would use Condition 2 that has parents verbalize arguments based on assigned topics that are most persuasive rather than allowing them to generate arguments based on chosen topics that may be less persuasive. If there is an effect of choice but not processing, we would use Condition 3 that has parents choose argument topics they want to hear rather than having them go through the more taxing process of generating their own. If both have an effect, Condition 1 will be selected for Stage 3.

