**Stage 1. Aim 1a:** We will recruit 42 parents of unvaccinated adolescents & 11 parents of adolescents who initiated the series. The RA will show the parent how to use a tablet-based application (a short video will provide HPV vaccine info suited for parents of adolescent females & males). The RA will use a series of questions to prompt parents to verbalize pro-vaccine arguments. Parents will then be asked to listen to, rate, and choose among *peer-generated* arguments. Finally, participants will be given the entire set of arguments. We will use probes to determine whether they can distinguish among and select their preferred arguments. **Aim 1b:** We will recruit 53 parents of unvaccinated adolescents with upcoming clinic appointments. We will audiorecord parent-provider discussions. Afterwards, parents will be asked about their prior experience with this provider and whether the HPV vaccine was discussed during the visit. The RA will administer a survey about provider recommendations, HPV vaccine benefits/barriers, & perceived involvement in medical care.

**Stage 2. Aim 2:** We will randomly assign 168 undecided parents to 1 of 4 intervention conditions. Parents will use a tablet-based application to either verbalize their own arguments based on topics they choose (deep processing/high choice), verbalize arguments based on topics assigned to them (deep processing/low choice), listen to arguments based on topics they choose (shallow processing/high choice), or listen to arguments based on topics assigned to them (shallow processing/low choice). We will assess parents' perspective on the tablet application, self-persuasion condition, and how their beliefs/experiences shape feelings about the HPV vaccine. Adolescents who accompany their parents to the appointment at their Parkland clinic will be offered the 1st HPV vaccine dose from a Parkland nurse immediately after the exit interview.

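### Aim 2 lets baseline significance tests decide which demographic covariates are added and names neither resulting model as primary; one pre-specified model that includes adolescent sex would be a minor, nearly free improvement.

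*Combined protocol and SAP*

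**What the plan says.** Under Analysis Plan for Aim 2 (Quantitative Analysis), the conditions are first compared: "demographic characteristics will be compared at baseline via two-way ANOVA or chi-square tests, as appropriate". The consequence is "If groups differ on any of these variables, further analyses will be conducted both with and without these variables as covariates", and the stated purpose is "to determine whether these demographic variables are of relevance to group differences". The variables, the significance level and the version that counts are not given.

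The intentions model is specified separately: "Independent variables will be dummy-coded variables based on two main effects (choice: high = 0, low = 1; processing: deep = 0; shallow = 1), plus their interaction". Baseline intentions has its own condition: "If equivalence assumptions of initial scores and parallel regression slopes for the groups are met, baseline intentions will be included as a covariate". If those assumptions fail, repeated measures ANOVA replaces the model. Adolescent sex is not a listed term.

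Under Additional Procedures for Each Stage, the Stage 2 text says "we will randomly assign 168 undecided parents (of 84 girls & 84 boys) to 1 of 4 intervention conditions". That is an overall enrolment split. Neither the allocation ratio nor stratification of the randomisation is stated. For Aim 1a, by contrast, the sample is described as stratified by sex, and the Aim 1a analysis looks at outcomes by sex so that the arguments carried forward suit both boys and girls.

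The section on synthesis of quantitative and qualitative analyses then links an effect of processing only to Condition 2, of choice only to Condition 3, and of both to Condition 1. It does not say which model supplies those findings.

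**The concern.** The conditions are randomised, so any baseline difference between them is due to chance if the randomisation was sound. A p-value for such a difference does not measure whether the variable predicts intentions, which is the reason to adjust for it. The rule can therefore add an irrelevant variable and leave out a prognostic one that happens to be balanced.

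Sex shows the problem. The sponsor thinks it important enough to fix by quota, yet it reaches the model only if it counts among the demographic characteristics and happens to differ between conditions. If the randomisation did balance it within condition, the test could never select it.

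What is at stake is which result is read as the answer on each effect when the Stage 3 condition is chosen, and possibly some precision.

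**Working it through.** The plan gives no alpha, power, standard deviation or target effect for Aim 2, so there is no power figure to reproduce. The counts agree: 84 + 84 = 168.

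**Assumptions.** Equal allocation (168/4 = 42 per condition), so each main effect, averaged over the other factor, compares 84 with 84; two-sided 5% tests; SD 1.

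**1. How often the rule triggers by chance.** For k independent 5% tests the chance of at least one significant result is 1 - 0.95^k. The plan does not state k.
- k = 5: 1 - 0.95^5 = 22.6%
- k = 10: 1 - 0.95^10 = 40.1%
- k = 15: 1 - 0.95^15 = 53.7%

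**2. How often it changes a conclusion.** A simulation used N = 168, 4,000 trials per setting and no true effect. Baseline intentions was always in the model and explained 30% of outcome variance. Six covariates explained 2% each, and sex explained 1%, 5% or 10%. Each covariate had one 5% test across the four conditions, and the effect of choice was then tested with and without the selected variables.
- A second model arose in about 30% of trials, as 1 - 0.95^7 = 30.2% predicts for seven tests. With sex balanced within condition it arose in 25-27% (1 - 0.95^6 = 26.5%).
- When it arose, the two models disagreed on significance in 2.5-3.7% of cases, which is about 1% of all trials.
- Taking the better of the two p-values gave a type I error of 0.035-0.055. The simulation error at 5% is sqrt(0.05 × 0.95/4000) = 0.0034, so inflation is not evident.

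These runs had no true effect. Disagreement when a real effect lies near the significance threshold was not simulated.

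**3. What a sex term could gain.** Let R² be the share of residual variance that sex explains; the documents give no value. The minimum detectable difference at 80% power is (1.960 + 0.842) × sqrt(1 - R²) × sqrt(2/84).

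| R² (assumed) | Detectable d | Power at d = 0.432 | Equivalent N, 168/(1 - R²) |
|---|---|---|---|
| 0 | 0.432 | 80.0% | 168 |
| 0.01 | 0.430 | 80.4% | 170 |
| 0.05 | 0.421 | 82.0% | 177 |
| 0.10 | 0.410 | 84.0% | 187 |

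The sections on enrolment say that only mothers will be analysed, and the Project Timeline shows 160 for Aim 2. With 80 against 80, the detectable d is 0.443 at R² = 0, 0.432 at 0.05 and 0.420 at 0.10, which is the same proportional gain.

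**4. If sex were balanced within condition but left out of the model.** In the same simulation, with sex explaining 5% or 10% of total outcome variance:
- The model standard error was 0.129 or 0.130, against a true 0.125 or 0.119.
- Type I error fell to about 0.043 or 0.033. With sex in the model it was 0.052 or 0.048.

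In this setting, omitting sex makes the test conservative.

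**5. Cost in degrees of freedom.** Intercept, choice, processing, interaction and baseline intentions leave 168 - 5 = 163. Adding sex leaves 162.

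**The case against.** The strongest defence is that the demographic step is a sensitivity check. The intentions model is specified separately, the version without demographics is always available, and the stated purpose is only to see whether those variables are relevant. Much of this stands. What remains is that neither version is labelled primary, while the Stage 3 choice needs a finding on each effect.

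Several stronger readings are tempting, and the documents do not support them:
- **That the tests choose every covariate.** Baseline intentions, probably the strongest predictor, is planned separately, subject to its own checks.
- **That sex is a stratification factor of the Aim 2 randomisation.** The 84/84 split is an enrolment quota, and a quota alone does not require adjustment.
- **That a second model is more likely than not.** Counting three tests per two-way ANOVA for 8 variables gives 1 - 0.95^24 = 71%. But 8 is an assumption, and the plan uses chi-square tests where appropriate. If 2 of the 8 were continuous and 6 categorical, there would be 2 × 3 + 6 = 12 tests and 1 - 0.95^12 = 46%.
- **That precision is certainly lost.** Nothing in the documents shows that sex predicts intentions.
- **That the regression alone picks the Stage 3 condition.** The choice also weighs new concerns, difficulty and completion time, and the investigators make it jointly.

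**Conclusion.** The point holds as a minor improvement to the plan; no error in the results has been demonstrated. A rule driven by chance imbalance cannot identify prognostic covariates, and the plan leaves open which of two models informs the Stage 3 choice. With 5 to 10 independent 5% tests, a second model would appear in about 23-40% of trials. Conflicting conclusions would be rare (about 1% in simulation with no true effect), and a reader should not infer that false positives are inflated. The gain from a sex term runs from nil to about 2-4 power points at R² of 0.05-0.10. The number of tests, their level and independence, equal allocation and every R² are assumptions.

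**What to change.** In the Analysis Plan for Aim 2:
- Report baseline demographics by condition descriptively, without significance tests.
- Name one primary linear model for intentions: choice, processing, their interaction, baseline intentions and adolescent sex.
- Keep baseline intentions in the model whatever a baseline-equivalence test shows. Randomisation makes the conditions equivalent in expectation, and a chance imbalance is when this adjustment is most useful.
- State that this model supplies the quantitative input to the Stage 3 choice, and report the model without sex as a sensitivity analysis.

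Interview language could be added but is optional; the plan names it only as a possible factor for parent participation in Aim 3. The cost is SAP wording and one degree of freedom for sex, with no new data.
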